8.5 Vital Signs

Vital signs include blood pressure (BP), heart rate, pulse oximetry, RR, and body temperature.

• Blood pressure and heart rate should be measured within 30 min before, and approximately (± 15 minutes) 1 hour after the completion of the first dose.

The subject's BP and heart rate should be captured after at least 5 minutes (+ 5 minutes) of rest while in a non-standing position (supine or semi-recumbent, head of bed from 0° to 90°). Subsequent vital sign measurements should be captured in the same non-standing position.

Systolic and diastolic BP will be measured using an automated calibrated device, with an appropriately sized cuff.

A pulse oximeter should be used to capture oxygen saturation.

Heart rate will be measured using an automated calibrated device, when available. If not available, heart rate will be measured manually.

Temperature will be obtained using an electronic (rapid reading) device whenever possible.

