5.2 Study Analysis Populations

5.2.1 Intent-to-Treat (ITT) Population

The ITT population will consist of all enrolled subjects regardless of whether the subject received test article.

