6.2 Demographics and Baseline Characteristics

Except where indicated, demographic data and baseline characteristics will be presented for the ITT population. A table will present the subject demographics (e.g., gender, age, ethnicity, and race) and baseline characteristics (height, weight, BMI, and creatinine clearance categorized before the start of test article as:

- severe renal impairment [< 30 mL/min],
- moderate renal impairment [30-50 mL/min],
- mild renal impairment [> 50-80 mL/min], and
- normal renal function [> 80 mL/min]).

Age will be calculated from the date of birth to the informed consent date. Age will be summarized as a continuous variable and in the categories, 18-45, >45-65, and >65 years.

Creatinine clearance will be calculated from the local laboratory data since these data were used for determination of the inclusion and exclusion criteria and will be determined from the Cockcroft-Gault equation.

A table will provide the frequency counts and percentages for subjects who received prior antibiotics, and PORT Risk Class (from the eCRF) for the ITT population. PORT score will also be summarized as a continuous variable.

Baseline assessments of clinical symptoms, clinical signs, abnormal vital signs, and abnormal laboratory signs of CABP will be presented for the ITT, and PK populations.

The number and percentage of subjects with each of the CABP symptoms (cough, pleuritic chest pain, dyspnea, and phlegm/sputum production) by severity (absent, mild, moderate, severe) will be presented. The number and percentage of subjects with the presence by severity (i.e., absent, mild, moderate, severe) of the following clinical signs will be provided: rales, rhonchi, dullness on percussion, bronchial breath sounds, wheezing, decreased breath sounds, and egophony. The number and percentage of subjects with fever (defined as body temperature > 38°C [100.4°F] oral or rectal), hypothermia (defined as body temperature < 36°C [95.5°F] oral or rectal), hypotension with systolic blood pressure < 90 mmHg, heart rate > 90 bpm, respiratory rate > 20 breaths/min, hypoxemia (defined as PaO₂ < 60 mmHg by arterial blood gas or oxygen saturation < 90% by pulse oximetry), elevated total WBC count (> 12,000 cells/mm³), leucopenia (WBC < 4,000 cells/mm³), elevated immature neutrophils (> 15% band forms regardless of total peripheral WBC count) and any of elevated total WBC count, leucopenia or elevated immature neutrophils will be summarized.

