8.2 Vital Signs

Vital signs include blood pressure (BP), heart rate, pulse oximetry, RR, and body temperature.

Descriptive statistics of the change from baseline to each post-baseline time point and the highest and lowest post-baseline value will also be provided. Baseline is defined as the value closest to but prior to the initiation of test article administration.

Post-baseline vital signs will be defined as clinically notable (CN) if they meet the criterion value or both the criterion value and the change from baseline criterion listed in Appendix 4. The incidence of CN vital signs will be summarized by time point and will be listed and flagged in by-subject listings. The overall post-baseline incidence of CN values for each vital sign parameter, which includes values from unscheduled post-baseline visits, will also be summarized. A listing will also be provided of subjects with a CN vital sign and will list all values for a vital sign noted as CN.

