9.3 Clinical Outcomes

The number and percentage of subjects classified as a Clinical Success, Clinical Failure, and Indeterminate by the Investigator's Assessment at EOT in the ITT population will be presented. The number and percentage of subjects in each response category for the overall assessment of Clinical response at PTE (based on the investigator's assessment) in the ITT population will also be presented. The number and percentage of subjects with stabilization of all vital signs associated with CABP at EOT will be presented for the ITT population as will the number and percentage of subjects with stabilization of each vital sign. These include temperature (no fever or hypothermia), SBP (> 90 mmHg), heart rate (< 90 bpm), RR (< 20 breaths/minutes), and PaO₂ (> 60 mmHg by pulse oximetry or ABG). WBC count (< 12,000 cells/mm³ or \geq 4,000 cells/mm³) and immature neutrophils (< 15%).

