10 DATA HANDLING CONVENTIONS

10.1 Premature Withdrawal and Missing Data

If available, pharmacokinetic parameters from the concentration-time profile data of patients who drop out or are withdrawn will be calculated but will be excluded from the final statistical analysis.

For all variables, only the observed data from the patients will be used in the statistical analyses, i.e., there is no plan to estimate missing data, unless otherwise specified.

Missing data occurs when any of the requested data is not provided, leading to blank fields on the collection of the instrument. These data will be indicated by the use of a "blank" in subject listing displays. Answers such as "Not applicable" and "Not evaluable" are not considered to be missing data and such be displayed as such.

All missing and partial dates for adverse events or for medications received after enrollment will be queried for a value. If no value can be obtained, substitutions will be made as detailed in Appendix 2. These substitutions will be used in calculations; however, the actual value recorded on the eCRF will be used in all listings.

Missing start and stop times for prior and concomitant antibiotics will be queried for a value. If no value can be obtained but the site indicates the antibiotic was received (onset time) prior to the first dose of test article, 00:01 will be used for the onset time. If the site also indicates that the end time was prior to the first dose of test article, 00:01 will be used for end time. The actual value (blank) will be recorded on the eCRF and will be used in the listings.

Subjects with the designation of treatment relationship of adverse event (AE) and serious adverse events (SAEs) missing will have the worst case assumed to impure the relationship: if relationship to study treatment is missing it will be assumed to be "Yes". The severity and causality assessment for adverse events cannot be missing. Missing data will be queried for a value.

Missing times for assessments of CABP symptoms will be queried for a value. If minutes are not available, the time will be recorded to the closest hour.

If no value can be obtained for all other times for events and assessments occurring after enrollment, the time will not be imputed but will remain missing.

For clinical response, missing data will be handled as follows: For investigator's assessment of Clinical Response at the EOT and PTE Visits:

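### SAP 9.3's WBC stabilization rule is met by every count and its oxygenation rule gives no limit for a saturation; separately, the printed 36.0°C and 95.5°F hypothermia limits disagree

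*SAP*

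**What the plan says.** SAP 9.3 (Clinical Outcomes) promises the number and percentage of subjects with "stabilization of all vital signs associated with CABP at EOT will be presented for the ITT population", and the same for each sign. It then lists the limits. The relevant stretch reads "60 mmHg by pulse oximetry or ABG). WBC count (< 12,000 cells/mm³ or", after which come a lower WBC limit of at least 4,000 cells/mm³ and a limit for immature neutrophils. The 60 mmHg limit is on PaO2 and is a strict greater-than.

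Other parts of the documents bear on these limits:

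- SAP 6.2 defines abnormal WBC as "elevated total WBC count (> 12,000 cells/mm³), leucopenia (WBC < 4,000 cells/mm³".
- SAP 6.2 defines "hypoxemia (defined as PaO₂ < 60 mmHg by arterial blood gas or oxygen saturation < 90% by pulse oximetry", so mmHg goes with blood gas and percent with oximetry.
- Protocol 8.5 states: "A pulse oximeter should be used to capture oxygen saturation".
- The Schedule of Events (Appendix 1 in both documents) has pulse oximetry at EOT but lists arterial blood gas (ABG) at Screening only.
- SAP 9.2 (Clinical Stability) accepts saturation of at least 90% or PaO2 of at least 60 mmHg, on room air.
- Inclusion criterion 4 (Synopsis and Protocol 6.2) and the hypothermia definition in SAP 6.2 give the lower temperature limit as below 36.0°C, with 95.5°F in brackets.

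**The concern.** A stabilization rule should separate subjects whose abnormality has resolved from those in whom it has not. The WBC rule cannot do that, because nothing fails it. The oxygenation rule cannot be applied to the measurement the study will normally hold at EOT. That leaves a programmer to choose a reading after the data exist, although SAP Section 1 says decisions about the final analysis are made before database freeze.

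The temperature pair is a different matter. It gives an eligibility criterion two limits that do not coincide, and the same pair defines hypothermia in the SAP baseline table. SAP 9.3 then relies on that definition when it requires absence of fever or hypothermia.

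**Working it through.** **1. WBC.** The inputs are the two limits in SAP 9.3 (below 12,000; at least 4,000; joined by *or*) and the abnormal ranges in SAP 6.2 (above 12,000; below 4,000).

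A count fails an *or* rule only if it fails both limits, that is, if it is at least 12,000 and also below 4,000. No number does.

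| Count (cells/mm³) | SAP 9.3 as printed | Abnormal under SAP 6.2 | At least 4,000 and at most 12,000 |
|---|---|---|---|
| 500 | passes | yes | fails |
| 1,500 | passes | yes | fails |
| 3,999 | passes | yes | fails |
| 4,000 | passes | no | passes |
| 8,000 | passes | no | passes |
| 12,000 | passes | no | passes |
| 12,001 | passes | yes | fails |
| 25,000 | passes | yes | fails |

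Over all integer counts from 0 to 100,000, the printed rule passes 100,001 of 100,001. Changing only *or* to *and* passes 8,000 (4,000 to 11,999). The exact complement of SAP 6.2 passes 8,001 (12,000 − 4,000 + 1). The two corrected versions differ only at 12,000, which SAP 6.2 does not call abnormal.

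**2. Oxygenation.** The inputs are the SAP 9.3 limit (PaO2 above 60 mmHg by oximetry or blood gas), the oximeter's output under Protocol 8.5 (saturation) and the schedule (oximetry at EOT, blood gas at Screening only).

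- For a subject with oximetry only, the item needs a value in mmHg and the record holds a percentage. SAP 9.3 gives no percentage limit, so there is no valid result.
- The composite requires every sign to be stable. If another sign fails, the subject is not stabilized whatever the oxygenation value. If every other sign passes, the subject cannot validly be classed as stabilized.
- If the unit were ignored and the percentage compared with 60, saturations of 61% to 89% would pass although SAP 6.2 calls them hypoxemia. That is 89 − 61 + 1 = 29 whole-percent values.

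**3. Temperature.** The printed equivalence is 36.0°C = 95.5°F. It does not reproduce:

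- °F = 36.0 × 9/5 + 32 = 96.8.
- °C = (95.5 − 32) × 5/9 = 35.28.
- Gap = 96.8 − 95.5 = 1.3°F, or 1.3 × 5/9 = 0.72°C.

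A reading from 95.5°F to below 96.8°F is hypothermia by the Celsius limit and not by the Fahrenheit limit. At 0.1°F resolution that is 13 readings (95.5 to 96.7). At 0.1°C it is 7 (35.3 to 35.9).

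The other clinical pairs convert correctly: 38.0°C to 100.4°F, 35°C to 95°F, 40°C to 104°F, and 37.8°C to 100.04°F (printed as 100).

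**The case against.** The strongest reply is that these are drafting slips in a descriptive table, that the intent is plain, and that the same information appears elsewhere. Much of that stands. Efficacy is an exploratory objective, and Protocol 12.8 plans no formal comparisons. EOT white counts also appear in the descriptive statistics, shift tables and listings of SAP 8.3. The shift grades do miss low counts, because SAP Appendix 3 puts 1,000 to 10,999 in Grade 0. Oxygenation at EOT is also judged, with usable units, under SAP 9.2.

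It could also be said that SAP 9.3 specifies no WBC row, since the WBC text is a fragment without a verb, and that each limit may answer its own baseline abnormality. The documents do not state that reading. Under it, a subject who was leucopenic at baseline and has 25,000 at EOT would still pass.

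A reader might infer more than the documents support, in four ways:

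- **That the WBC fault corrupts the vital-sign composite.** SAP 8.2 says "Vital signs include blood pressure (BP), heart rate, pulse oximetry, RR, and body temperature", and in SAP 9.3 a full stop separates WBC from the signs before it.
- **That up to all 30 planned subjects would have no composite result.** SAP 10.1 says "only the observed data from the patients will be used in the statistical analyses", but it has no rule that one missing component voids a composite. A subject who fails another sign is already not stabilized. The table is for the ITT population, and "The ITT population will consist of all enrolled subjects regardless of whether the subject received test article", so unevaluable subjects could also stay in the denominator as not stabilized. SAP 10.1's Indeterminate rule covers clinical response only.
- **That 29 saturations, or 13 or 7 temperatures, measure expected misclassification.** They show the width of the gaps on a measurement grid, not numbers of subjects.
- **That the temperature error will admit or exclude many subjects.** It changes eligibility only if a site applies the Fahrenheit figure, the reading falls in the gap, and exactly one of the other three vital signs is abnormal, since two of four are required.

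**Conclusion.** All three faults are in the text and the arithmetic is certain. None looks like an extraction fault: the connector is a printed word, the mismatched method is printed in full, and 95.5°F appears in three places across two documents.

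- **WBC:** any summary programmed as written gives 100% of subjects with an EOT value as stabilized, so it carries no information.
- **Oxygenation:** the item has no valid result for oximetry-only subjects, and such a subject cannot validly be called stabilized on the composite. The number affected depends on unscheduled blood gases and on failures of other signs, neither of which can be known from the documents.
- **Temperature:** two limits 1.3°F apart stand in one eligibility criterion and one baseline definition. Any effect on enrolment rests on the assumption that a site uses the Fahrenheit figure. The documents place the sites in the US but give no recording unit.

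The first two faults are confined to one exploratory descriptive EOT summary. The primary AUC(0-48) analysis is unaffected. The text should be corrected because it is wrong as written and cheap to put right, not because a main conclusion is at risk.

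**What to change.** **SAP 9.3, WBC.** Write the limit as at least 4,000 and at most 12,000 cells/mm³, the complement of SAP 6.2. Complete the sentence so that it says what will be tabulated.

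**SAP 9.3, oxygenation.** Pair unit with method: saturation of at least 90% by pulse oximetry, or PaO2 of at least 60 mmHg by blood gas. State whether the room-air condition of SAP 9.2 applies here, and which value governs when a subject has both. Say also how a subject with no usable oxygenation value is counted in the composite.

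**Temperature.** The sponsor must reconcile the 36.0°C and 95.5°F pair to one threshold in inclusion criterion 4 (Synopsis and Protocol 6.2) and in SAP 6.2. This review does not say which figure was intended. The temperature item in SAP 9.3 then follows.

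**Cost.** The SAP changes are a few words made before database freeze, with no new data. The protocol change is one figure in two places, but Protocol 13.6.2 requires a written amendment for it.

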10 DATA HANDLING CONVENTIONS

10.1 Premature Withdrawal and Missing Data

If available, pharmacokinetic parameters from the concentration-time profile data of patients who drop out or are withdrawn will be calculated but will be excluded from the final statistical analysis.

For all variables, only the observed data from the patients will be used in the statistical analyses, i.e., there is no plan to estimate missing data, unless otherwise specified.

Missing data occurs when any of the requested data is not provided, leading to blank fields on the collection of the instrument. These data will be indicated by the use of a "blank" in subject listing displays. Answers such as "Not applicable" and "Not evaluable" are not considered to be missing data and such be displayed as such.

All missing and partial dates for adverse events or for medications received after enrollment will be queried for a value. If no value can be obtained, substitutions will be made as detailed in Appendix 2. These substitutions will be used in calculations; however, the actual value recorded on the eCRF will be used in all listings.

Missing start and stop times for prior and concomitant antibiotics will be queried for a value. If no value can be obtained but the site indicates the antibiotic was received (onset time) prior to the first dose of test article, 00:01 will be used for the onset time. If the site also indicates that the end time was prior to the first dose of test article, 00:01 will be used for end time. The actual value (blank) will be recorded on the eCRF and will be used in the listings.

Subjects with the designation of treatment relationship of adverse event (AE) and serious adverse events (SAEs) missing will have the worst case assumed to impure the relationship: if relationship to study treatment is missing it will be assumed to be "Yes". The severity and causality assessment for adverse events cannot be missing. Missing data will be queried for a value.

Missing times for assessments of CABP symptoms will be queried for a value. If minutes are not available, the time will be recorded to the closest hour.

If no value can be obtained for all other times for events and assessments occurring after enrollment, the time will not be imputed but will remain missing.

For clinical response, missing data will be handled as follows: For investigator's assessment of Clinical Response at the EOT and PTE Visits:

 Subjects will be defined as an Indeterminate if the investigator cannot determine whether the subject is a Clinical Success or Failure at the EOT or PTE Visits or the subject has a missing response. By definition, subjects with an Indeterminate response are included in the denominator for analyses in the ITT population, and thus, are considered Clinical Failures.

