8.11.1 PK Blood Collection and Processing

Blood Collection (plasma):

Blood samples will be collected and analyzed for omadacycline concentration at the following times:

- Day 1: within an hour prior to Dose 1, 1, 1.5, 2, 2.5, 3, 4, 6, 8, 12 hours (12 hour taken immediately before Dose 2);
 Dose 2 administered (times relative to Dose 1); 13, 13.5, 14, 14.5, 15, 16, 24 hours post dose
- Day 2: within an hour prior to dose, 1, 1.5, 2, 2.5, 3, 4, 6 hours
- Day 3: prior to the Day 3 dose
- EOT: anytime during the visit

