8.20 Subject Discontinuation or Withdrawal

Reasons why a subject may discontinue or be withdrawn from the study include, but are not limited to, AE, lost to follow up, withdrawal by subject, physician decision, death, and other (specify reason eg, subject non-compliance or study termination by the sponsor). Subjects may voluntarily withdraw from the study for any reason at any time. Subjects are considered withdrawn from the study if they state an intention to withdraw, or fail to return for visits, or become lost to follow up for any other reason. If premature withdrawal from the study occurs for any reason, the investigator should determine the primary reason for a subject's premature withdrawal from the study and record this information on the eCRF.

Subjects who discontinue study treatment should not be considered withdrawn from the study (unless the subject withdraws informed consent). The date and primary reason for discontinuation of study treatment should be recorded. Subjects who discontinue study treatment prematurely should complete the EOT visit, PTE visit and Final Follow-up Assessment, if possible (see Schedule of Events - Appendix 1). The site should also collect subject safety information through the Final Follow-up assessment.

Site personnel should also contact the IxRS, if used to register the subject's discontinuation from test article.

For subjects who are lost to follow up, the investigator should show "due diligence" by documenting in the source documents steps taken to contact the subject, eg, dates of telephone calls, registered letters, etc.

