9.4.2 Final Follow-up

The FFU assessment should be conducted within 30-37 days following the subject's first dose of test article. This evaluation should also be conducted for any prematurely withdrawn subject with the exception of subjects who withdraw consent. The Final Follow-up assessment may be conducted via telephone contact or by another interactive technology for subjects who are a Clinical Success and had no AEs or clinically significant laboratory, or ECG abnormalities noted at or after the PTE visit. Otherwise, the visit must be conducted in person.

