12.2 Determination of Sample Size

This study is designed to evaluate the PK profile of an oral dosing regimen, 300mg BID on Day 1 and QD on Day 2, in adults with CABP. The sample size determination is based on consideration of the precision of the estimate, GMR of AUC₍₀₋₄₈₎ for 300mg po to 100mg IV, derived from model-based simulations of omadacycline concentration data (Phase I studies).

With 20 evaluable subjects, there will be 90% probability that the 90% CIs of the GMR for $AUC_{(0-48)}$ will be within 80% and 125%. Up to 30 subjects will be enrolled so that at least 20 subjects are evaluable for bioavailability estimation.

The number may be adjusted as needed to meet this requirement.

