5.2.3 Pharmacokinetic (PK) Population

The pharmacokinetic population is defined as subjects who receive test article and have at least 1 evaluable PK parameter. If any subject has an emesis within 4 hours after dosing, the subject will be excluded from PK Analysis. If any subject discontinues dosing before 48 hours with incomplete PK profile for 0-24 or 0-48 hours, the subject will be excluded from the PK analysis for AUC_{0-24} and AUC_{0-48} , respectively.

This population will be used for listings, summary tables, and plotting of individual and mean/median concentration-time profiles.

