7.3 Treatment Comparison

The comparison of interest is the comparative bioavailability assessment between the test, 300mg po in CABP patients, and the reference, 100mg IV in healthy subjects. The comparison will be based on 90% confidence intervals (CIs) for the geometric mean ratios (GMR) of AUC (0-48) for the two dosing regimens being within 80% and 125%.

The PK parameter data for 100mg IV in healthy subjects comes from PTK 0796-SDES-0501(n=5), PTK 0796-BEQU-0801(n=11), PTK 0796 WOIV-0703(n=12), CPTK796A2104(n=21), CPTK796A2201(n=6), PTK 0796-RENL-15102(n=8). Using the

day 1 plasma concentration profile of the 100mg IV QD dosing from these studies, a BID dosing on day 1 and a QD dosing on day 2 was simulated using the superposition principle. The simulation model-based AUC $_{(0-48)}$ characteristics for each study are shown in the table below:

Study	n	Mean ln (AUC (0-48))	SD ln (AUC (0-48))
SDES-0501	5	9.5968	0.1896
BEQU-0801	11	9.8702	0.1467
WOIV-0703	12	10.017	0.1630
A2104	21	10.043	0.1649
A2201	6	10.129	0.1752
RENL-15102	8	10.039	0.1838
Total	63	9.9800	0.2091

The 90% CI of the GMR will be formed as follows: let \bar{y} , *s*, and *n* represent the average, standard deviation, and sample of the log (AUC (0-48)) data observed in the current study. The

pooled standard deviation is $s_p = \sqrt{\frac{(63-1)0.2091117^2 + (n-1)s^2}{63+n-2}}$; the number of degrees of freedom is df = 63 + n - 2; and critical value for the CI is 95th percentile of a t-distribution, $t_{df.0.95}$. The 90% confidence interval on the log scale is

$$\bar{y} - 9.980044 \pm t_{df,0.95} s_p \sqrt{\frac{1}{63} + \frac{1}{n}} = (Lower, Upper)$$

and the CI for the GMR is $(e^{Lower}, e^{Upper}) \times 100\%$.

The following SAS code will be used:

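### Read literally, SAP 10.1 and Protocol 12.7 drop a complete AUC0-48 when a subject withdraws weeks later; nothing says that the narrower rule in SAP 5.2.3 takes precedence

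*SAP*

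**What the plan says.** **The withdrawal rule.** SAP 10.1 and Protocol 12.7 share one sentence. PK parameters, if available, from "patients who drop out or are withdrawn will be calculated but will be excluded from the final statistical analysis". Neither section says when the withdrawal must occur or what happens if the profile is already complete.

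**The PK population rule.** SAP 5.2.3 has a narrower criterion: "If any subject discontinues dosing before 48 hours with incomplete PK profile for 0-24 or 0-48 hours", the subject leaves the analysis of the corresponding AUC. Emesis within 4 hours of dosing is a separate exclusion. On use, the section says: "This population will be used for listings, summary tables, and plotting of individual and mean/median concentration-time profiles". The ratio comparison is not listed.

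**The comparison.** SAP 7.3 compares AUC0-48 in this study with 63 historical healthy subjects, using a pooled-SD 90% confidence interval and limits of 80% to 125%. It describes the test data only as those observed in the current study. It then announces SAS code, which does not appear in the text available to us.

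**Timing.** The last sample needed for AUC0-48 is "Day 3: prior to the Day 3 dose" (Protocol 8.11.1). Protocol 8.20 counts subjects as withdrawn if they state that intention, fail to return for visits, "or become lost to follow up for any other reason". It also says that stopping treatment is not in itself withdrawal. Protocol 9.4.2 says: "The FFU assessment should be conducted within 30-37 days following the subject's first dose of test article".

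**Sample size.** Protocol 12.2 and SAP 5.1: "Up to 30 subjects will be enrolled so that at least 20 subjects are evaluable for bioavailability estimation".

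**The concern.** The exposure that AUC0-48 measures is fixed once the Day 3 pre-dose sample is drawn. A subject who moves away in week 3 or misses the final visit still has exactly the same AUC0-48. A rule that lets such an event remove the value from the main comparison discards valid primary data.

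Two programmers could also reach different subject counts from the same plan. One would take 10.1 as governing, because it is the section that speaks of the final statistical analysis. The other would take 5.2.3 as governing, because it is specific to AUC. The comparison in SAP 7.3 is the only confidence interval in the plan, so its membership should not depend on which section was read first.

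**Working it through.** **Step 1: one subject under each rule.** Take a subject with every sample through the Day 3 pre-dose draw and no emesis, who continues dosing and is lost to follow-up on Day 20.

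| Section | Trigger | AUC0-48 |
|---|---|---|
| SAP 10.1, Protocol 12.7 | Drop-out or withdrawal at any time | Calculated, then excluded |
| SAP 5.2.3 | Dosing stopped before 48 h and profile incomplete | Kept |

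SAP 12 records the new definition of the PK set and its emesis rule. It does not mention the withdrawal sentence.

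**Step 2: how long the rule stays open.** Final follow-up at 30-37 days after first dose, minus 2 days of profiling, leaves 28 to 35 days in which a withdrawal could remove a finished profile.

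**Step 3: reproduce the plan's figures.**
- *Reference summary.* The six study rows in SAP 7.3 give n = 63 and a weighted mean of 9.9801. The within-study sum of squares is 1.5851 and the between-study sum is 1.1277, so SD = √[(1.5851 + 1.1277)/62] = 0.2092. The SAP prints 9.9800 and 0.2091, which agrees within rounding.
- *The stated 90% probability at 20 subjects.* This cannot be reproduced uniquely, because neither document gives the assumed true ratio or the patient SD. By normal approximation it corresponds to a common SD of about 0.264 at a true ratio of 1, or to a true ratio of about 0.936 at SD 0.2091. It is not shown to be wrong.

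**Step 4: precision.** Inputs are the reference n of 63 and SD of 0.2091117 (SAP 7.3), with the patient SD assumed equal to the reference SD. The documents give no late-loss rate, so losses of 1, 2 or 3 from 20 are assumed.

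Half-width on the log scale = t(0.95, 61 + n) × 0.2091117 × √(1/63 + 1/n)

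- n = 20: 1.6639 × 0.2091117 × 0.2567 = 0.0893
- n = 17: 1.6646 × 0.2091117 × 0.2733 = 0.0951

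The interval at an observed ratio of 1 is exp(± half-width). The last two columns give the probability that the interval lies within 80-125% at a true ratio of 1 (2,000,000 simulations). The reference is either held fixed at its published summary or resampled.

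| n | Half-width | Increase | Interval at ratio 1 | Reference fixed | Reference resampled |
|---|---|---|---|---|---|
| 20 | 0.0893 | – | 91.5-109.3% | 99.6% | 98.7% |
| 19 | 0.0911 | 2.0% | 91.3-109.5% | 99.4% | 98.4% |
| 18 | 0.0930 | 4.2% | 91.1-109.8% | 99.2% | 97.9% |
| 17 | 0.0951 | 6.5% | 90.9-110.0% | 98.8% | 97.4% |

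**Step 5: less favourable assumptions.** With the reference resampled, going from 20 to 18 subjects lowers the probability from 93.7% to 91.9% at a true ratio of 0.95 (SD 0.2091), and from 91.3% to 88.8% at a patient SD of 0.30 (ratio 1). Both settings are assumptions.

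**The case against.** **The sentence may be meant narrowly.** It opens conditionally, covering parameters only if they are available. That fits subjects who leave during profiling, and a specific rule such as 5.2.3 would usually prevail over a general convention. This is plausible, and it is why the point is an over-broad rule in tension with 5.2.3 and not a strict contradiction. But the limit is not written down.

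**The plan does indicate a set for the comparison.** A reader might infer that the primary comparison has no analysis population at all. The documents do not support that. SAP 5.1 ties the confidence interval of the ratio to subjects evaluable for the PK population, and SAP 7.2 summarises AUC0-48 on the PK Analysis Set. The code that SAP 7.3 announces might also name the set, but we cannot see it. This part of the objection stands. What remains is that the visible text of 7.3 does not name the set, and that pointing to the PK population does not settle whether 10.1 then removes subjects from it.

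**The trigger is narrow and the sample size can be adjusted.** Stopping treatment is not withdrawal, and some final follow-ups may be done by telephone. Enrolment may be adjusted to reach 20 evaluable subjects: if 23 complete sampling and 3 are dropped, 20 remain. This also stands, with one reservation. Protocol 8.20.1 sets its replacement target in terms of complete PK sampling, which a subject lost after the last sample has already met. The safeguard therefore works only if evaluability is counted after late withdrawals are known.

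**Bias.** A reader might infer that the rule distorts the ratio. That would require late withdrawers to differ in 0-48 h exposure, and the documents contain nothing to show that they do.

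**Conclusion.** The concern holds as a wording defect in a rule that bears on the main comparison. Taken literally, SAP 10.1 and Protocol 12.7 discard complete AUC0-48 values that SAP 5.2.3 would keep, and no text gives 5.2.3 precedence. The textual finding rests on no assumption.

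The size is small. With 1 to 3 assumed late losses from 20, the interval widens by 2.0% to 6.5% on the log scale. The chance of meeting the limits falls by at most 1.3 percentage points at SD 0.2091 and a true ratio of 1 (98.7% to 97.4%, reference resampled). The assumed less favourable settings cost 1.8 to 2.5 points for a loss of 2. These figures do not support a claim that the study is underpowered. The reason to act is that the correction is free, keeps valid data and settles membership before database freeze. It should be made.

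**What to change.** 1. Replace the withdrawal sentence in SAP 10.1 with: *Drop-out or withdrawal from the study does not by itself exclude a PK parameter; the Section 5.2.3 exclusions apply identically to all subjects, whether or not they later withdraw.*
2. Add to SAP 7.3: *The AUC0-48 comparison uses all PK-population subjects with an evaluable AUC0-48 under Section 5.2.3.*
3. Record the departure from Protocol 12.7 in SAP 12. Protocol 12.1 already allows changes to the analyses to be described in the SAP.

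The words *apply identically* matter. A rule that excluded withdrawn subjects whenever their profile was incomplete would drop someone lost on Day 20 for one missed sample, yet keep a subject with the same gap who stayed in the study. Withdrawal status would then still decide inclusion.

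The cost is one replaced sentence, one added sentence and one line in the change log. No new data are needed, and the emesis and incomplete-profile exclusions stay as they are.
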